#### **9.3.1.1. Further Details of the MMRM Analysis**

The mixed model for repeated measures (MMRM) model will be fitted using SAS PROC MIXED procedure with restricted maximum likelihood estimation, an unstructured covariance matrix, and the Kenward-Roger approximation for denominator degrees of freedom. The unstructured covariance is the least restrictive and generally performs well with limited number of repeated measures per patient and puts no parameters on the data with respect to the covariance structure assumptions.

- Only in the unlikely circumstance that there are convergence problems with the MMRM analysis will other covariance structures be examined to resolve the convergence issue, ie, we would evaluate other additional variance-covariance structures, including compound symmetry (CS), heterogeneous compound symmetry (CSH), and auto-regressive [AR(1)]. In this eventuality, the Akaike’s Information Criterion (AIC) will be used to determine the optimal variance-covariance structure matrix for the primary comparisons.
  - If convergence issues arise, the base by visit interaction may be dropped.

*Sample* SAS code is as follows. The actual SAS code may be modified as appropriate. Note that the treat\*region interaction will be assessed for significance (at alpha 0.10), and if not significant, will be dropped from the model.

```
ods trace on;
```

```
Proc mixed data=MMRM1 method=reml PLOTS (MAXPOINTS=200000000000);
  class usubjid trt avisitn region;
  model chg=trt avisitn trt*avisitn trt*region base basemmsescore
base*avisitn region /ddfm=kr;
  repeated avisitn/subject=usubjid type=un r;
  lsmeans trt*avisitn/pdiff cl ;
  lsmeans trt*region/pdiff alpha =0.10;
  ods output lsmeans=_LS diffs=_lsdiff tests3 =tst;
run;
ods trace off;
```

### 9.3.2. Description of Missing Data for the Primary Efficacy Endpoint

The patterns of missing data will be presented, with the number (%) of patients in each treatment group with each pattern of missingness, as demonstrated in Table 15. These data will be examined to determine if there was any general difference in the pattern of missing data between the treatment groups, as well as to explore the assumption of missingness at random. Note that for the primary efficacy endpoint, data were only collected at baseline, Week 4, and Week 24, and thus the patterns would be presented accordingly.

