CAF	X		X					X		X		X		
UPDRS-III			X	X		X						X	X	
CSI			X							X		X		

Abbreviations: ADAS-Cog = Alzheimer’s Disease Assessment Scale; ADCS-ADL = Alzheimer’s Disease Cooperative Study – Activities of Daily Living; CAF = Clinician’s Assessment of Fluctuation; CDR System= Cognitive Drug Research computerized assessment system; CIBIS = Clinician’s Interview-Based Impression of Severity; CIBIC+ = Clinician’s Interview-Based Impression of Change Plus caregiver Interview; COWAT = Controlled Oral Word Association Test; CSI = Circadian Sleep Inventory; C-SSRS = Columbia-Suicide Severity Rating Scale; CT = computed tomography; DS = Dependence Scale; ECG = electrocardiogram; EQ-5D-5L = EuroQual five dimensions questionnaire, five level version; Hep = hepatitis; IP = investigational product; LBCRS = Lewy Body Composite Risk Score; MMSE = mini-mental state examination; MRI = Magnetic Resonance Imaging; NEVHI = North East Visual Hallucinations Inventory; NPI = Neuropsychiatric Inventory; PET = positron emission tomography; SPECT = single-photon emission computed tomography; TSH = thyroid stimulating hormone; UPDRS-III = Unified Parkinson’s Disease Rating Scale, Part III

1. The Single-Blind Run-In Period may be extended for 1 to 10 days for subjects who do not meet MMSE stability criterion for randomization. If, after the first extension to the Single-Blind Run-In Period, the subject still does not meet the MMSE stability criterion for randomization, the run-in period may again be extended for an additional 1 to 10 days. No more than 2 extensions to the Single-Blind Run-In Period will be allowed. Subjects who require one extension to the run-in period will have a new Baseline visit occurring no more than 10 days after the originally intended Baseline at Visit 3. Subjects who require two extensions to the run-in period will have a new Baseline visit occurring no more than 20 days after the originally intended Baseline at Visit 3. No new IP will be dispensed for the extended run-in periods; subject should be instructed to continue taking blinded IP dispensed at Visit 2.

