An independent Safety Monitoring Committee (SMC) will review interim safety data accumulated after approximately 30 subjects have completed 4 weeks of double-blind treatment and throughout the study at points specified in the SMC Charter. The SMC will provide their recommendation regarding the acceptability of reducing the visit frequency by omitting certain visits (Visits 5, 7 and 9) for both newly enrolled subjects and subjects active in the study at the time of the recommendation. Study enrollment will not be stopped or slowed to wait for SMC's recommendation and will proceed as planned with all visits until the SMC recommendation is made. Site will be formally notified of the SMC's recommendation regarding whether Visits 5, 7 and 9 can be omitted. [The meeting did occur and the SMC recommended Visits 5, 7, and 9 be omitted.]

After completion of Visit 12, the subject may be considered for enrollment in the extension study RVT-101-2002. If the subject does not enter the extension study, he/she will return for the Safety Follow-up Visit (Visit 13). Subjects who enter the extension study will not be required to complete Visit 13.

A study schema is shown in [Figure 1](#) and study scheduled assessments are presented in [Table 2](#).

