#### **7.4. Analysis Populations**

It is intended that a complete accounting of patients for the analysis populations will be provided, from the Screening Population through the Per-Protocol Population.

- Screening Population: All patients who are screened (signed an informed consent) will be included in the Screening Population.
- Placebo Run-In Population: All patients who took at least 1 dose of IP in the Placebo Run-in will be included in the Placebo Run-In Population. This population will be used to provide an accounting of the disposition of patients during this phase of the study.

- Randomized Population: The Randomized Population will include all patients who are randomized.
- Safety Population: All subjects who were randomized and took at least one dose of double-blind investigational product.
- Intent-to-Treat (ITT) Population: All subjects randomized to treatment who have taken at least one dose of double-blind investigational product and who have a baseline and at least one post baseline primary efficacy assessment for the UPDRS-III **or** for the ADAS-Cog 11. This will be the primary population used for the efficacy analysis of all variables EXCEPT the UPDRS Part III and Part 5.
- UPDRS Primary Analysis Population: This will be the primary population used for the UPDRS Part III efficacy analysis, and is comprised of all ITT patients EXCLUDING those with no change OR a worsening in UPDRS-III total score prior to a dose increase in anti-parkinsonian medication (including but not limited to L-dopa, dopamine agonists, and monoamine oxidase inhibitors) and where there is *subsequent* improvement or stabilization of UPDRS-III total score.
  - Dose increase in anti-parkinsonian medication is defined as an increase in dose, dose frequency or commencement of anti-parkinsonian medication where the total daily dose of anti-parkinsonian medication at Week 24 is higher than at Baseline.
- UPDRS Sensitivity Analysis Population: All ITT patients EXCLUDING those who increase or start anti-parkinsonian medication treatment during the double-blind treatment period.
  - Dose increase in anti-parkinsonian medication is defined as an increase in dose or frequency or commencement of anti-parkinsonian medication where the total daily dose of anti-parkinsonian medication at Week 24 is higher than at Baseline.

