#### 9.3.4.3. Multiple Imputation

Missing data for the primary endpoint will be imputed utilizing multiple imputation methods. Multiple imputation provides a useful strategy for analyzing data sets with missing values. Instead of filling in a single value for each missing value, Rubin's [Rubin 1976, Rubin 1987] multiple imputation strategy replaces each missing value with a set of plausible values that represent the uncertainty about the correct value to impute.

The nature of missing data will be explored and the extent of missing data pattern (over time) will be summarized.

The assumption that data are missing at random (MAR) is common to the above analyses. To examine the primary endpoint with an analysis that does not require the MAR assumption, a pattern-mixture approach will be utilized for the imputation. The first step will be to apply a Markov chain Monte Carlo (MCMC) method [Schafer 1997] that assumes multivariate normality will be used to impute all missing values to make the imputed (resulting) data sets have strictly monotone missing patterns. The resulting monotone missing pattern will then, in a second imputation step, be used to impute the remaining missing values; specifically, a regression-based pattern-mixture method for continuous variables will be applied.

The SAS software system will be used to perform this imputation. Because the imputation of missing data is a key aspect to the analysis of the data, explicit details regarding this imputation are provided via sample SAS code that is intended to demonstrate the application of these strategies. Variable definitions are:

- TRT=treatment group (1 or 0)

- Eff1 is the first time point for the variable score
- Eff2 is the second time point for the variable score
- Eff\_last is the last time point for the variable score. Additional variable scores (between Eff1 and Eff\_last) would be included in this model according to the time points for collection.

The first step will be to impute partially in order to obtain a monotone missing data pattern.

```
proc mi data=DATAIN out=DATAIN_MONO nimpute=100 seed=123;  
  var TRT Eff1 Eff2 ... Eff_last;  
  mcmc chain=multiple impute=monotone;  
run;
```

The second step will be to impute the remaining (monotone) missing data that is MAR for each of the 100 imputed datasets from the first step.

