Following the imputation of the data to create a monotone missing pattern, missing values for the earliest missing value (visitnum1) are imputed BY VISIT (thus, one imputation at a time), using the covariates basescore, MMSEbase score, geographic region, and previous score (ie, the non-missing score from previous visit). The first visit to be imputed (as necessary) would be the Week 4 time point, then the Week 24 time point. Thus, the process is repeated sequentially, by visit, until the monotone missing data pattern is completely filled in (imputed). In the case of the secondary endpoint, in which values are collected more frequently, there will be more ‘calls’ to the PROC MI procedure to generate the final imputed dataset. The following sample SAS code demonstrates the general methodology for imputing the first visit (Week 4) and second visit (Week 24) for UPDRS- III data. Note that the output dataset from the first imputation is used as the input dataset for the second imputation.

```
**First procedure imputes missing values for the first visit (Week 4);  
proc mi data=DATAIN_MONO out=DATAREG1 seed=465 nimpute=1;  
  by _Imputation_;  
  var visitnum1 bascore MMSEbase region previous;  
  monotone regression(visitnum1);  
run;  
  
** Second procedure imputes missing values for the second visit (Week 24)  
proc mi data=DATAREG1 out=DATAREG2 seed=465 nimpute=1;  
  by _Imputation_;  
  var visitnum1 visitnum2 bascore MMSEbase region previous;  
  monotone regression(visitnum2);  
run;
```

Note that the regressions do not include the treatment variable, and thus the imputed data at each time point will be based on the distribution of all data in the model rather than treatment-group specific distributions.

- A total of 100 imputed datasets will be created using these imputed data.
- Each of the 100 imputed datasets will then be analyzed using the MMRM model with effects for treatment, mmsebase score, region, and bascore. In this way, the test of the efficacy endpoint at Week 24 will be obtained, once for each of the 100 imputed datasets.
- The 100 resulting treatment effect parameters and standard errors from these will be combined to provide a distribution of parameters (and standard errors) upon which the sensitivity analysis will be concluded. PROC MIANALYZE may be used for this summary of the analysis.

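### SAP 9.3.2 and 9.3.4.3 leave Week 1 out of the UPDRS-III visits although both schedules mark it; the missing-data description and the multiple imputation need reconciling with the schedules

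*SAP*

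**What the plan says.** SAP 9.3.2, on the description of missing data for the primary endpoint, states: "Note that for the primary efficacy endpoint, data were only collected at baseline, Week 4, and Week 24", and adds that the missing patterns will be shown to match those three times. SAP 9.3.4.3 uses the same set for the multiple imputation: "The first visit to be imputed (as necessary) would be the Week 4 time point, then the Week 24 time point". Its sample code is introduced as "imputing the first visit (Week 4) and second visit (Week 24) for UPDRS- III data", with one PROC MI call for each.

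The schedules differ. The UPDRS-III row of Protocol Table 2 reads "UPDRS-III X X X X X". Read against the visit header, the five marks fall at V3 (baseline), V4 (Week 1), V6 (Week 4), V12 (Week 24) and V13 (Week 26 follow-up). The row in SAP Table 2 has the same five positions. The one change to the visit plan is recorded in SAP Section 3: "The meeting did occur and the SMC recommended Visits 5, 7, and 9 be omitted". Visit 4 is not among those dropped.

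SAP 7.4 admits to the ITT Population a randomized, dosed subject with a baseline and "at least one post baseline primary efficacy assessment for the UPDRS-III" or for the ADAS-Cog 11. The UPDRS Primary Analysis Population is a subset of ITT.

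**The concern.** The SAP contradicts its own schedule, and the protocol's, about when the primary endpoint was measured, and two pieces of planned work follow the shorter list. The pattern table is meant to compare missingness between arms and to explore whether data are missing at random. If Week 1 is left out, subjects lost between Week 1 and Week 4 cannot be told apart from subjects with no post-baseline motor score. The imputation is the SAP's check on the missing-at-random assumption. If Week 1 is not a visit in it, the only on-treatment motor score of the earliest leavers may go unused there, while LOCF on the same endpoint would use it.

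**Working it through.** **1. The plan's own figure.** The visit question does not bear on the power statement, which reproduces. With 70 per group, difference 4, SD 7.5 and two-sided alpha 0.05 (SAP Section 6): SE = 7.5 × √(2/70) = 1.268; 4/1.268 − 1.960 = 1.195; Φ(1.195) = 0.884. The noncentral t with 138 df gives 0.880. The plan states 88%.

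**2. Post-baseline times for UPDRS-III, side by side.**

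| Source | Wk 1 | Wk 4 | Wks 12, 18 | Wk 24 | Wk 26 |
|---|---|---|---|---|---|
| Protocol Table 2, UPDRS-III row | yes | yes | no | yes | yes |
| SAP Table 2, UPDRS-III row | yes | yes | no | yes | yes |
| SAP 9.3.2 text | no | yes | no | yes | no |
| SAP 9.3.4.3, visits imputed | no | yes | no | yes | no |
| SAP Table 15, example shell | yes | yes | yes | yes | no |

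SAP Table 14 also keeps a Week 1 analysis window (study days 2 to 10). A slipped column in the extracted tables is an unlikely explanation: each schedule row carries five marks and SAP 9.3.2 allows three. Leaving Week 26 off an on-treatment list is defensible, because under SAP 7.7.2 an efficacy assessment more than 7 days after the last dose counts as follow-up.

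**3. Effect on the pattern table.** With baseline present, two on-treatment times give 2² = 4 patterns; three give 2³ = 8.

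**4. One subject followed through: Week 1 score present, lost before Week 4.**
- *ITT membership.* ADAS-Cog is first scheduled after baseline at Week 12, and neither scale is marked in the early-termination column. The Week 1 UPDRS-III is therefore the only scheduled on-treatment assessment that can admit this subject.
- *Pattern table.* Weeks 4 and 24 are both missing, so the subject appears to have no post-baseline motor data.
- *LOCF (SAP 9.3.4.2).* The Week 1 score is carried to Week 24.
- *Imputation (SAP 9.3.4.3).* Week 4 is imputed from baseline score, baseline MMSE, region and a covariate `previous`, described as the non-missing score from the preceding visit. If that is taken as baseline, it duplicates a term already listed and Week 1 is unused. If it is taken as Week 1, Week 1 enters as a predictor. The first stage says that further scores "would be included in this model according to the time points for collection", which would admit Week 1 only if it is recognised as a collection time; SAP 9.3.2 says it is not.

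Even on the favourable reading, no step fills a missing Week 1 score. One is needed for a subject who enters ITT through ADAS-Cog without a Week 1 or Week 4 UPDRS-III.

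**5. Size.** The documents give no dropout rate and no between-visit correlations, so these inputs are assumptions: 80 per arm, 10 without Week 24, of whom 0, 2, 4 or 8 leave between Week 1 and Week 4; SD 7.5. The information on the three visit means is the sum over missing patterns of n × Σ⁻¹ for the visits observed, and the Week 24 variance V is the last diagonal element of its inverse. Power is Φ(4/√(2V) − 1.96). The table gives the ratio of the Week 24 standard error with Week 1 to that without it.

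| Correlations W1–W4, W1–W24, W4–W24 | 0 early | 2 early | 4 early | 8 early |
|---|---|---|---|---|
| 0.5, 0.3, 0.5 | 0.9998 | 0.9988 | 0.9977 | 0.9955 |
| 0.7, 0.5, 0.6 | 0.9992 | 0.9964 | 0.9935 | 0.9875 |
| 0.8, 0.7, 0.8 | 0.9993 | 0.9935 | 0.9876 | 0.9753 |

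The gain runs from 0.02% to 2.5% of the standard error. In power it runs from 0.8936 to 0.8937 at one end, and from 0.8895 to 0.9039 (1.4 points) at the other. This is a known-covariance calculation. It indicates how much information Week 1 carries and does not simulate the SAP's imputation.

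**The case against.** The best defence is that little depends on the note. It governs only how missing patterns are displayed, and the Table 15 shell already has a Week 1 column. The imputation code is offered as a sample of the general method. Because `previous` is listed separately from the baseline score, it adds something at the Week 4 step only if it means Week 1. LOCF already uses Week 1 for the very subjects in question, and SAP 8.1 plots time to discontinuation by arm, so early dropout would be visible elsewhere. Finally, SAP 9.3.2 is in the past tense and SAP 9.3.4.3 agrees with it, so the schedules could be the part that is wrong.

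Much of this stands. The imputation text is ambiguous and does not clearly exclude Week 1, and the documents show a conflict without showing which side is true. Three things survive. Table 15 is a generic example that also shows Weeks 12 and 18, when UPDRS-III is not scheduled, so it cannot settle the visit list. SAP 9.3.2 expressly ties the displayed patterns to the shorter list. And the discontinuation plot shows when subjects left, not which of them have a motor score.

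**Conclusion.** The inconsistency is real, lies within the SAP as well as between SAP and protocol, and should be corrected. Its reach is limited to the missing-data description and the multiple-imputation sensitivity analysis. The likely effect on the Week 24 estimate is small: about 0% to 2.5% of the standard error under the assumptions above, with the stated 88% power untouched.

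A reader might infer three stronger things that the documents do not support.
- *That the primary analysis discards Week 1.* SAP 9.3.1 uses the observed responses at each visit, and its code lists no visits. The Wilcoxon test runs at each scheduled visit and LOCF takes the last non-missing value. None is expressly restricted to Weeks 4 and 24.
- *That early leavers lose all their information in the imputation.* Baseline score, MMSE and region remain in it on any reading, and Week 1 may enter through `previous`.
- *That the schedules must be right.* No passage says that Week 1 was dropped, but none confirms that it was collected.

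**What to change.** Before unblinding, establish whether UPDRS-III was collected at Visit 4, and reconcile SAP 9.3.2 and 9.3.4.3 with both schedules.

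If it was collected:
- State the on-treatment UPDRS-III visits as Weeks 1, 4 and 24. This also puts the visit levels of the MMRM beyond doubt.
- Show those visits in the UPDRS-III version of Table 15 and drop Weeks 12 and 18 from it.
- Run the sequential imputation as Week 1, Week 4, Week 24.
- Define `previous` as the score at the preceding collected visit.

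If it was not collected, correct the UPDRS-III rows of both schedules instead, and note that a subject lost before Week 4 would then have no scheduled on-treatment assessment that qualifies for ITT.

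The cost is a few lines of SAP text and, in the first case, one more PROC MI call. Sample size and the primary model terms do not change.

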**Table 15: Examples of Patterns of Missingness (Study RVT-101-2001)**

Pattern	Treatment Group	Number (%) of Patients	Baseline	Week 1	Week 4	Week 12	Week 18	Week 24
1	Intepirdine 35mg	xx (xx.x%)	X	X	X	X	X	.
	Intepirdine 70mg	xx (xx.x%)	X	X	X	X	X	.
	Placebo	xx (xx.x%)	X	X	X	X	X	.
2	Intepirdine 35 mg	xx (xx.x%)	X	X	X	X	.	.
	Intepirdine 70mg	xx (xx.x%)	X	X	X	X	.	.
	Placebo	xx (xx.x%)	X	X	X	X	.	.
Etc.								

### 9.3.3. Wilcoxon Rank Test

Analysis using a non-parametric (distribution-free) Wilcoxon Rank Sum Test will be performed. This analysis will be performed for each protocol-scheduled visit using the observed cases change from baseline data. *Sample* SAS code is as follows. The actual SAS code may be modified as appropriate.

```
Proc npar1way data=dat;
  By visit;
  Class treat;
  Var chg_from_baseline;
  ods select WilcoxonScores
```

### 9.3.4. Sensitivity Analysis from Imputation of Missing Efficacy Data for Primary Efficacy Endpoint

#### 9.3.4.1. Cumulative Distribution Function

A cumulative distribution plot of changes in scores from baseline to Week 24 will be provided, with percent of patients on Y-axis and change score on X-axis.

#### 9.3.4.2. Last Observation Carried Forward

An ANCOVA model will be run on the Week 24 data for which any missing values at Week 24 are imputed from last non-missing value carried forward (LOCF) for a given patient. If there are no on-treatment values for a patient, the baseline (last pre-treatment) observation will be carried forward.

*Sample* SAS code is as follows (where bascore is the baseline score for the endpoint and center is the pooled geographic region variable.

```
Proc Mixed data=dat;  
  Class treat MMSEbase center;  
  Model outcome=treat mmsebase center bascore;  
  Run;
```

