### **8.3.1.4. Clinician's Interview-Based Impression of Severity (CIBIS) and Clinician's Interview-Based Impression of Change Plus Caregiver Interview (CIBIC+)**

The CIBIC+ assessment ([Schneider et al., 1997](#)) measures the global functioning of the subject through structured interviews with both the subject and caregiver. The Clinician's Interview-Based Impression of Severity (CIBIS) will be administered at Baseline and the CIBIC+ will be administered at subsequent study visits. The change from Baseline is recorded on a 7-point scale with a score of 4 indicating no change, scores above 4 indicating worsening, and scores below 4 indicating improvement. This scale will be administered by a rater who is trained and certified

for this study, and who is independent of other cognitive and functional rating scales. Every effort should be made to have the same CIBIS/CIBIC+ rater for each subject for the duration of the study.

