### **5.3. Clinician’s Interview Based Impression of Change Plus Care Giver Interview (CIBIC+)**

The CIBIC+ assessment [[Schneider 1997](#)] measures the global functioning of the subject through structured interviews by an investigator with both the subject and caregiver. The CIBIC+ is a secondary endpoint in this study. CIBIS is the baseline version.

The CIBIC+ is recorded on a 7-point scale with a score of 4 indicating no change, scores above 4 indicating worsening, and scores below 4 indicating improvement.

The CIBIC+ scale is a single item instrument, if the CIBIC+ is not done at a visit or the result is missing at a visit, the result will be set to missing. There is no ‘change from baseline’ calculated (eg, using the CIBIS). The CIBIC+ is analyzed by-visit using the observed values.

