#### 9.4.1. Secondary Efficacy Endpoint Analyses

The secondary efficacy analyses endpoints are the change from baseline in the ADAS-Cog 11 score at Week 24, and the observed scores of the CIBIC+ at Week 24.

This will be analyzed using similar MMRM methods as the primary endpoint (however, for the CIBIC+, no baseline value or interaction with visit will be included). A Wilcoxon Rank test will also be performed, as will the sensitivity analysis for LOCF to Week 24 and multiple imputation. The sensitivity analyses as being performed on the primary endpoint (CDF, LOCF, and multiple imputation) will be performed for the secondary endpoints.

For the CIBIC+, The number and percentage of subjects in each category of CIBIC+ will also be summarized by visit for each treatment group and tested using a CMH RMS test.

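### The SAP extends the LOCF baseline fallback and baseline covariate to CIBIC+, a change rating with no baseline value, and gives no rule for that case

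*SAP*

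**What the plan says.** - **SAP 9.3.4.2 (LOCF)** fits an ANCOVA at Week 24 with missing values filled by the last non-missing one, and then states: "If there are no on-treatment values for a patient, the baseline (last pre-treatment) observation will be carried forward". The sample code has treatment, baseline MMSE, pooled region and a term bascore, explained by the words "where bascore is the baseline score for the endpoint".
- **SAP 9.4.1** names as secondary endpoints the ADAS-Cog 11 change and "the observed scores of the CIBIC+ at Week 24". It then says: "The sensitivity analyses as being performed on the primary endpoint (CDF, LOCF, and multiple imputation) will be performed for the secondary endpoints". Its one exception for CIBIC+ is a parenthesis attached to the MMRM: "for the CIBIC+, no baseline value or interaction with visit will be included".
- **SAP 5.3** says "The CIBIC+ is recorded on a 7-point scale with a score of 4 indicating no change", and also "CIBIS is the baseline version". It adds that no change score is formed from the CIBIS and that a CIBIC+ not done at a visit is set to missing.
- **Protocol 8.3.1.4** says the CIBIS "will be administered at Baseline and the CIBIC+ will be administered at subsequent study visits".
- **Table 2 in both documents** has CIBIS at V3 only and CIBIC+ at V6, V8, V10, V11 and V12. The early termination (ET) column has no CIBIC+.

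**The concern.** The fallback was written for a score measured on the same scale before and after treatment. For UPDRS-III and ADAS-Cog 11, carrying baseline forward means zero change, which is a clear if debatable assumption. CIBIC+ has no such baseline. The one rating available before treatment measures a different thing, severity rather than change, so a programmer who follows the rule to the letter would mix two constructs in one outcome variable. A programmer who sees that this makes no sense has no written alternative. The baseline covariate in the same model has the same problem.

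At stake is the credibility of a robustness check on a secondary endpoint. If the handling is settled only after unblinding, the check loses the value of having been pre-specified.

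**Working it through.** **1. Does the fallback reach CIBIC+?** Yes, on the text. SAP 9.3.4.2 exempts no endpoint, and SAP 9.4.1 extends LOCF to the secondary endpoints as a group. The CIBIC+ exception in 9.4.1 concerns MMRM terms, whereas LOCF uses a separate ANCOVA.

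**2. What would be carried?**

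| Endpoint | Rating before treatment | What the fallback yields |
|---|---|---|
| UPDRS-III | same scale, V3 | zero change |
| ADAS-Cog 11 | same scale (from ADAS-Cog 13), V3 | zero change |
| CIBIC+ | none; CIBIS only | a severity rating, or nothing |

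On the CIBIC+ scale the counterpart of zero change is a score of 4.

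**3. Can a subject be in this position?** ITT entry (SAP 7.4) needs a baseline and one post-baseline UPDRS-III or ADAS-Cog 11; it does not need a CIBIC+. Table 2 schedules UPDRS-III at V4 (Week 1) and the first CIBIC+ at V6 (Week 4). A subject who leaves between the two is in the ITT population with no CIBIC+, and none is scheduled at ET. SAP 9.3.2 conflicts with this: it says UPDRS-III was collected only at baseline, Week 4 and Week 24. On that schedule the Week 1 route closes, and the case remains only for a subject with a Week 4 UPDRS-III but no CIBIC+.

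**4. The covariate.** CIBIC+ has no baseline score to put into bascore. Unlike the fallback, this touches every subject in the CIBIC+ LOCF model.

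**5. Size.** The plan's own CIBIC+ power reproduces. With a difference of 0.5, SD 0.95 and 80 per group:

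- Standard error = 0.95 × √(2/80) = 0.150
- 0.5 / 0.150 = 3.33
- Power = Φ(3.33 − 1.96) = 91.5% (91.1% with the t distribution), against 91% stated

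The documents give neither the share of subjects without any CIBIC+ nor any CIBIS values, so what follows is illustration only. Assume arm means of 4.0 (active) and 4.5 (placebo), shares m_A and m_P with a carried value, and the same mean carried value v in both arms. Then:

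D = [(1 − m_P) × 4.5 + m_P × v] − [(1 − m_A) × 4.0 + m_A × v]

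| m_A / m_P | v = 3 | v = 4 | v = 5 |
|---|---|---|---|
| 5% / 5% | 0.475 | 0.475 | 0.475 |
| 10% / 10% | 0.450 | 0.450 | 0.450 |
| 10% / 5% | 0.525 | 0.475 | 0.425 |
| 5% / 10% | 0.400 | 0.450 | 0.500 |

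Carrying v instead of 4 changes D by (m_P − m_A) × (v − 4). With equal shares this is zero. With shares of 10% and 5% and v one point from 4, it is 0.05 × 1 = 0.05 points in either direction, which is 0.05 / 0.5 = 10% of the planning effect.

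**The case against.** The strongest reply is that no sentence in either document orders a CIBIS score to be carried into CIBIC+. The LOCF rule sits under a heading for the primary endpoint. SAP 5.3 declines to form a change from CIBIS and sets a missed CIBIC+ to missing, and SAP 9.4.1 keeps a baseline value out of the CIBIC+ MMRM. A sensible programmer would conclude that there is nothing to carry.

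Much of this stands. A reader might infer that the SAP instructs the substitution of CIBIS. It does not: that result comes only from combining the fallback with the remark in 5.3 about the baseline form, and other text points away from it. But the reply does not close the gap. The missing-value sentence in 5.3 governs the score at a visit, and LOCF exists precisely to fill such values. The exception in 9.4.1 is worded for the MMRM. Nothing says what the LOCF analysis does with these subjects.

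Three other inferences are tempting and not supported:

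- **That severely affected subjects would be counted as worsened and mild ones as improved.** Neither document gives the range, direction or midpoint of CIBIS.
- **That a definite share of the treatment effect is at risk.** Every input to such a figure would be assumed.
- **That the CMH test is affected too.** Week 24 LOCF data for that test appear only in the protocol synopsis. SAP 9.4.1 describes the CMH test without LOCF, and SAP 7.3 gives the SAP precedence.

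**Conclusion.** The point holds as a rule that does not work for this endpoint. As written, the fallback either picks up a severity rating or cannot be carried out, and the covariate has no value to take.

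It is a minor point. It reaches one sensitivity analysis of one secondary endpoint. The fallback matters only for ITT subjects with no on-treatment CIBIC+, mainly those who leave very early; their number is not given. The UPDRS-III analysis and the observed-data CIBIC+ MMRM are unaffected.

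The size and direction of any bias cannot be derived from the documents. The illustration shows only that, if the mean carried value is the same in both arms, the choice of value drops out when early loss is equal and matters when it is not. That the case arises through a Week 1 UPDRS-III rests on Table 2 being right over SAP 9.3.2.

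**What to change.** Add to SAP 9.3.4.2 and 9.4.1, before unblinding:

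- CIBIC+ has no baseline value, and CIBIS is never carried forward as a CIBIC+ value.
- In the LOCF analysis, a subject with no on-treatment CIBIC+ is assigned 4 (no change), and the number so assigned is shown by arm.
- bascore is dropped from the CIBIC+ LOCF ANCOVA.

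Assigning 4 mirrors the zero change that the rule already implies for UPDRS-III and ADAS-Cog 11. Leaving these subjects missing would also be defensible, but it would treat CIBIC+ differently from the other two endpoints. SAP 9.3.2 and Table 2 should be reconciled on the Week 1 UPDRS-III at the same time.

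The cost is a few sentences and minor code, with no new data. The downside is that no change is itself an assumption, though it is the one the SAP already makes for the other two endpoints.
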